On the day of each visit, participants will be instructed to take the morning resveratrol dose 30 minutes prior to the visit; time of dosing will be recorded. Levels will be taken at 90 minutes post-dose.

Spirometry (all visits)

Spirometry will be performed at all visits, using EasyOne spirometer (ndd Medical Technologies, Zurich), in accordance with American Thoracic Society (ATS) and European Respiratory Society (ERS) standards and using predicted values from Global Lung Initiative (GLI) 2012.^{104,105} Each participant will use the same spirometer during the entire study period.

Before spirometry testing, respiratory medications will be withheld according to the following schedule: long-acting anticholinergic agents, 24 hours; short-acting beta-agonists, 4 hours; short-acting theophyllines and long-acting beta-agonists, 12 hours; and once daily theophyllines 48 hours.

At all visits, pre-bronchodilator spirometry will be performed initially, followed immediately by 400 μ g of salbutamol given by volumatic spacer device. Reversibility will be tested by measuring spirometry after 15 minutes.

Health-related quality of life (HR-QoL) questionnaires (Visits 2 and 4)

Three different HR-QoL questionnaires will be used, to assess differing but common symptoms experienced by patients with bronchiectasis.

- The *St George's Respiratory Questionnaire (SGRQ)* is validated for use in bronchiectasis and includes 56 items (76 weighted responses) across 3 domains - symptoms, activity and impact.^{106,107} Component scores from each domain and a total score will be examined. The total score is between 1 and 100; high scores indicate poor health. Thresholds for a clinically significant change in health status using SGRQ

are: i) a difference of 4 units, which indicates effective treatment ii) a difference of 8 units, which indicates very effective treatment.¹⁰⁸

- The *Bronchiectasis Health Questionnaire (BHQ)* is the most recent HR-QoL questionnaire developed for use in bronchiectasis. It consists of 10 items, with higher scores corresponding to better HRQoL.¹⁰⁹ It has very good internal consistency and strong convergent validity with the SGRQ. Strengths of the BHQ include easy interpretation, using a single total health score, and availability in 11 different languages (English, French, Spanish, Dutch, German, Italian, Japanese, Mandarin, Belgian, US-Spanish and US English).
- The *Leicester Cough Questionnaire (LCQ)* is a further HR-QoL questionnaire, developed for patients with chronic cough, which is a key symptom for patients with bronchiectasis. The LCQ consists of 19 items, is self-administered and assesses three domains over the preceding two weeks: physical, psychological and social. Total severity score ranges from 3 to 21; a lower score reflects worse quality of life relating to cough. It is validated for use in bronchiectasis and scores correlate with SGRQ. The minimal clinically important difference for LCQ is 1.3 points.^{110,111}
- *Medical research council (MRC) breathlessness score and modified MRC (MMRC)* are brief, single answer questionnaires that quantify a patient's degree of breathlessness. They have been widely administered for a range of respiratory conditions since the MRC was developed in 1952, which evolved into MMRC.¹¹² MMRC score is a component of important markers of severity scoring systems in bronchiectasis.¹¹³

Food frequency questionnaire (Visit 2)

The amount of resveratrol in the study product far exceeds dietary intake, but it is important to consider the contribution of dietary resveratrol and other dietary antioxidants to overall levels and antioxidant status.

In a large study of 40,685 individuals, the mean dietary resveratrol intake in Spain was 194 µg/day. In this population, the highest source of resveratrol was red wine, followed by other wines, fresh grapes, grape juice, peanuts and pistachios.¹¹⁴ The highest levels are found in red wines (up to 14.3 mg/L), considerably lower than the doses used in this study.³⁶ Interestingly, annual red wine consumption in Spain and NZ is similar (21.7L and 20.3L per capita per year respectively).¹¹⁵

Similarly, a wide range of other antioxidants are available from dietary sources. The antioxidant content of different foodstuffs has been studied in great detail and dietary intake of antioxidants may impact on many diseases, including bronchiectasis.²⁹

We will assess variation in antioxidant intake in study participants using a food frequency questionnaire (FFQ), developed for this study. Our FFQ will focus on foodstuffs containing high levels of antioxidants, and foodstuffs that account for most variation in antioxidant intake.¹¹⁶⁻¹¹⁸ The FFQ will also specifically ask participants about their intake of the ten foodstuffs/food groups containing the highest quantities of resveratrol.^{114,119-123}

Participants will be divided into tertiles according to their reported intake, classified as “highest”, “moderate” or “lowest” consumers, based on their responses. Two scores will be calculated: an “Overall Antioxidant Score” and a “Resveratrol Score”. Scoring for all questions will range from 0 to 8 (0 for “never or less than once per month”; 8 for “6+ times per day”). All questions will be included for the “Overall Antioxidant Score”. The 10 foodstuffs containing resveratrol are annotated with the letter “R” on the questionnaire. Scoring will be performed in identical fashion for these ten items to provide the “Resveratrol Score”.

Diary cards (screening to visit 4)

Symptoms will be recorded using daily diary cards and will be reviewed at each clinic visit. Symptom severity (cough, wellbeing, sputum volume, sputum colour, dyspnoea) will be recorded. Use of community-based services, and any associated costs paid by patients themselves, will be recorded in the daily diary card. This will include services provided by GPs, practice nurse, physiotherapists and any other primary health providers that patients access directly. Sputum colour will be assessed using a validated and reliable sputum colour chart which is available for use in bronchiectasis.^{100,101} Details including descriptive features will be located in the diary card.

Phone contact (weeks 2 and 8)

Patients will be contacted by telephone in between visits to remind them of follow up appointments and completion of diary cards, to discuss adherence to study medication, and to record any exacerbations or adverse events.

Patients will also be instructed to contact study staff if they have been admitted to hospital. Pulmonary exacerbation will be defined in accordance with an international consensus agreement: “a deterioration in three of more of the following key symptoms for at least 48 hours, in at least three of: cough, sputum volume and/or consistency, sputum purulence, breathlessness and/or exercise tolerance, fatigue or malaise, haemoptysis – AND a clinician determines that a change in bronchiectasis treatment is required”.¹²⁴

These key symptoms will make up the patient diary card discussed above, helping to standardize pulmonary exacerbation diagnosis. Information on the use of any hospital-based services will be recorded by study personnel. Full details of any treatments received in the hospital setting will be recorded from their electronic medical record.

Tolerability will be recorded dichotomously and defined as successful completion of the study. Adherence will be described as percentage of capsules taken calculated from prescribed and returned medication. We will record participation consent probability, recruitment and drop-out events.

End points

Primary end point: Change in sputum neutrophil elastase

Secondary end points:

- Sputum hs-CRP
- Sputum cytokines – GM-CSF, IL-1 β , IL-6, IL-8, TNF- α
- Sputum purulence
- Sputum cathelicidin (LL-37)
- Sputum procalcitonin
- Sputum culture
- Sputum and serum total antioxidant capacity
- Sputum and serum resveratrol levels (and metabolites)
- Pulmonary exacerbation frequency
- Lung function (spirometry: FEV1, FVC)
- Health-related quality of life
 - St George’s Respiratory Questionnaire
 - Bronchiectasis Health Questionnaire
 - Leicester Cough Questionnaire
- Adverse events
- Adherence, tolerability and safety of oral resveratrol supplementation
- Requirement for induction of sputum at Visit 4

Statistical Methods

Analysis plan

The analysis will take place in an intention-to-treat analysis set. Our primary aim is addressed by the hypothesis that the primary outcome (*sputum neutrophil elastase levels*) at visit 4 will decline from high values at visit 2 (baseline), or remain stable from low values at visit 2. Accordingly, the primary analysis will consist in a regression of the change at visit 4 from baseline on the value at baseline, using a suitable parametric model, a flexible smooth model for the baseline value and appropriate adjustments (including adjustments for dosage in interaction with baseline).

The alternative hypothesis then translates as a negative relationship between baseline and difference at visit 4. The model is provisionally identified as lognormal, inferred from the literature, but a data review will be effected to confirm.

Safety data will be reported in detail by arm and stratified by severity and causality, using Common Terminology Criteria for Adverse Events (CTCAE) standard. *Tolerability and adherence* will be regressed on the dosage arm using logistic and linear regression respectively. As this is a signal-finding study, tests will be conducted at a significance level of 10% against two-sided alternatives, with no adjustment for multiplicity.

Sample size

We have based our sample size on the baseline values from two highly important papers assessing neutrophil elastase levels in bronchiectasis.^{11,101} One study reported median sputum neutrophil elastase levels of 15 µg/ml (IQR 3-23 µg/ml); in the other, levels varied according to stable or exacerbation state, with median of 0.39 µg/ml (IQR 0-23.5 µg/ml).^{11,101} Converting these values to approximate mean and standard deviation using standard techniques yielded estimated lognormal parameters on which we based our simulations. With these parameters and assuming a drop-out rate of 10%, we ran extensive power simulations to establish a detectable decrease at visit 4 from baseline of 40% with 80% power (under any dosage). The detectable difference corresponds to a decrease from 5 to 3 µg/ml between baseline and visit 4. The same sample size enables us to detect a doubling of the efficacy of resveratrol under the 2000 mg vs 1000 mg per day dosage with 80% power, provided the larger dose decreases sputum neutrophil elastase by 67% or more.

Data Monitoring Committee

A data monitoring committee will comprise 3 external members.

- *[name]* (Biostatistician, Ko Awatea, Counties Manukau DHB; Independent) – Chair of committee
- *Assoc. [name]* (Respiratory Physician, Western Health, Melbourne; Co-investigator)
- *[name]* (Respiratory Physician, Department of Respiratory Medicine, Middlemore Hospital; Independent)

References:

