Study design:	Single centre, single-arm, pre-post, open-label study of oral resveratrol in adults with bronchiectasis, incorporating sub-study of participants randomised to receive either 500 mg twice daily, or 1000 mg twice daily
Study size:	40 participants
Target population:	Participants aged ≥18 years with bronchiectasis confirmed on CT chest, with ≥1 exacerbation in the preceding 12 months
Study drug:	Participants will take Transmax (resveratrol 500 mg + 5 mg piperine + 5 mg polydatin), either 1 capsule twice a day or 2 capsules twice a day
Duration of treatment:	12 weeks 4 visits: Screening [V1], baseline [V2], 4 weeks [V3], 12 weeks [V4]

Endpoints:

- *Primary endpoint:* Sputum neutrophil elastase
- *Secondary endpoints:* Sputum hs-CRP
Sputum cytokines
Sputum purulence
Sputum cathelicidin (LL-37)
Sputum procalcitonin
Sputum culture
Serum & sputum total antioxidant capacity
Serum & sputum resveratrol (+ metabolite) levels,
Serum hs-CRP
Tolerability
Adherence
Adverse events
Exacerbation frequency
Lung function (spirometry: FEV₁ and FVC)
Health-related quality of life (SGRQ, BHQ, LCQ)

Schedule of visits and procedures:

Visits	1	2	3	4
	Screening	Treatment		
	-4 to -2 wks	0 wks	4 wks	12 wks
Informed consent	X			
Demographics	X			
Eligibility criteria	X	X		
Medical history	X			
Physical examination	X	X	X	X
Vital signs, including weight	X	X	X	X
Spirometry	X	X	X	X
Randomisation to 500 mg or 1000 mg twice daily		X		
Blood tests				
FBC	X			X
U+E	X			X
LFT	X			X
hs-CRP		X		X
Cytokines (IL-1 β , IL-6, IL-8, GM-CSF, TNF- α)		X		X
Serum resveratrol levels		X		X
Serum total antioxidant capacity		X		X
Sputum analysis				
Neutrophil elastase		X	X	X
hs-CRP		X	X	X
Cytokines (IL-1 β , IL-6, IL-8, GM-CSF, TNF- α)		X		X
Sputum purulence		X		X
Sputum cathelicidin (LL37)		X		X
Sputum procalcitonin		X		X
Sputum culture		X		X
Sputum resveratrol levels		X		X
Sputum total antioxidant capacity		X		X
Pregnancy test if applicable (blood)	X			X
Urinary pregnancy test		X		X
Concomitant medication review	X	X	X	X
Record pulmonary exacerbations		X	X	X
Record adverse events			X	X
Health-related Quality of Life				
SGRQ		X	X	X
BHQ		X	X	X
LCQ		X	X	X
MRC & mMRC breathlessness grade	X			
Dietary questionnaires				
Food frequency questionnaire		X		
Issue diary cards	X			
Review and collect diary cards		X	X	X
Issue study medication		X	X	
Collect and account for study drug			X	X
Telephone contact		Weeks 2 and 8		

Background

The increasing importance of bronchiectasis in New Zealand

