 - A significant disease is one that would, in the opinion of the investigator, put the participant at risk through participation in the study, or a disease which may influence the results of the study, or the participant's ability to participate in the study.
- Patients with cystic fibrosis
- Patients with primary ciliary dyskinesia
- Patients with hypogammaglobulinaemia

- Patients with allergic bronchopulmonary aspergillosis (defined as the presence of asthma, total serum IgE > 1000 IU/ml, with detectable specific IgE to Aspergillus or positive Aspergillus skin test)
- Patients taking immunosuppressive agents (e.g. azathioprine, methotrexate, cyclophosphamide)
- Patients with other primary or acquired immunodeficiency
- Patients with evidence of active or suspected cancer and patients having undergone cancer treatment including resection, radiation therapy or chemotherapy within the last 2 years (patients with basal cell carcinoma and squamous cell carcinoma are allowed)
- Pregnant or lactating women
- Participation in a separate clinical or device trial within 4 weeks of screening
- Allergy to any of the components of Transmax

Reasons for discontinuation of study medication

- Participant request to discontinue treatment
- Adverse event that contraindicated further dosing, in the opinion of the investigator
- Risk to subject, as judged by the investigator
- Pregnancy
- Discontinuation of the study at the request of the Data Monitoring Committee or regulatory agency, institutional review board or independent ethics committee

Participants who prematurely discontinue treatment should continue in the study until the final visit, if possible. It is highly recommended that all study procedures, including any scheduled visits, are continued until the final visit, if possible.

Withdrawal of participants from the study

- Participant request to withdraw from study
- Lost to follow-up
- Investigators deem that participants are at significant risk of harm from study medication or procedures
- The Data Monitoring Committee requests patient withdrawal due to major safety concerns

Criteria for termination of the study

- Investigators deem that participants are at significant risk of harm from study medication or procedures
- Investigators reserve the right to terminate the study if adequate resources or funding are no longer available to continue the study

Study medication

Investigational products

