Substance:	Resveratrol 500 mg + piperine 5 mg + polydatin 5 mg (“Transmax”)
Form:	Capsule
Unit strength:	500 mg
Route of administration:	Oral

Dosage regimen

Oral resveratrol will be commenced at a dose of either 500 mg twice daily or 1000 mg twice daily.

Treatment will continue at this dose for the duration of the study (12 weeks). Patients will be advised to take the study product with food to maximize absorption.^{79,95}

Test drug dispensing

Participants will be issued with resveratrol at visits 2 (week 0) and 3 (week 4). 40 participants will each receive a blister pack supply of 500 mg capsules for 4 weeks at visit 2, and for a further 8 weeks at visit 3, according to the dosage regime to which they are allocated.

Participants will be advised to contact the research team if adverse effects develop. If adverse effects are experienced, patients can opt to *reduce by one dose step* after consultation at either a clinic visit or following telephone communication. Dose steps will be 2000 mg a day, 1000 mg a day and 500 mg a day.

Adherence will be monitored and measured by keeping a record of the number of tablets issued and returned. Patient's adherence with the proper use of the study drug will be assessed at visits 3 and 4, and patients will be reminded to bring all study medication pack(s) (used or unused) and completed diaries to these visits.

Packaging and labelling

Biotivia LLC, New York, USA will provide the capsules containing 500 mg resveratrol. The following will be printed on each compliance pack: trial number, medication number, packet number, participant initials, directions for use, expiry date, caution statement, storage instructions, space for "date dispensed", and name and address of host institution. All used trial medication packs are to be returned to the patient treatment box for drug accountability.

Concomitant Medications

Any medication that patients take other than the study drug, including herbal medicine or supplement, is considered as concomitant medication and must be recorded in the worksheets.

At screening (visit 1), patients will be asked about all medications they have taken during the last 12 months with special attention to the use of antibiotics, corticosteroids, antioxidant and dietary supplements, and bronchodilators. These should be reviewed at every subsequent study visit.

Safety Parameters

Adverse events

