An adverse event (AE) is defined as any untoward medical occurrence, including an exacerbation of an existing condition in a trial participant receiving a pharmaceutical product. The event does not necessarily have to have a causal relationship with this treatment.

A serious adverse event is defined as any AE which results in death, is immediately life threatening, results in persistent or significant disability, requires or prolongs participant hospitalisation, is a congenital anomaly or birth defect, or is an important medical event that may jeopardise the patient or require intervention to prevent one of the above outcomes.

It is the responsibility of the investigator to record and report all AEs (both serious and non-serious) occurring during the course of the clinical trial (from signing the informed consent form through to the end of the trial). It will be derived by spontaneous, unsolicited reports of patient, by observation and by routine open questionings such as "Has there been any change in your health since I last saw you".

All adverse events will be fully documented on the worksheet with the onset, intensity, seriousness, outcome and action taken, including change in dosage of study drug.

All serious adverse events and unexpected serious adverse reactions (SUSARs) will be reported to the study Data Monitoring Committee. The Health and Disability Ethics Committee (HDEC) do not require notification of SAEs and SUSARs but *urgent safety measures* (to protect participants from a serious, immediate hazard to their health and safety) will be notified to the HDEC within 7 days.

Clinical trial participants alert card

Participants will also be issued with a clinical trial participant's alert card containing information of the study and contact phone numbers of the study staff, to carry throughout the duration of the study.

Study Procedures

There will be 4 visits (screening [visit 1]; treatment commencement [visit 2]; 4 weeks [visit 3]; and 12 weeks [visit 4]).

There will be a 2-4 week baseline period between screening (visit 1) and commencing treatment (visit 2). At visit 2, patients will be randomised to receive either 500 mg twice daily, or 1000 mg twice daily. Participants will be randomized in a ratio of 1:1, with 20 participants in each group of the sub-study. Randomisation will be performed with the use of a computer-generated sequence with random block sizes of 2 and 4.

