Participants have to be clinically stable for at least 4 weeks with no event-based exacerbations before commencing treatment to ensure clinical stability.

Clinical assessment (visits 1, 2, 3, 4)

This will include documentation of subject characteristics, medications, and measurement of vital signs (pulse, blood pressure, and temperature at every visit. Physical examination (general, cardiovascular, respiratory, abdominal examinations) will be done by an investigator at all study visits.

Simple blood tests (visits 1 and 4)

Blood samples will be taken to measure full blood count (FBC), urea & electrolytes (U&E), liver function tests (LFT) and highly-sensitive C-reactive peptide (hs-CRP) at visits 1 and 4. For female participants of child-bearing potential, a serum β -hCG level (pregnancy test) will be measured at screening (visit 1). A urinary pregnancy test will be done at visit 2 prior to commencement of study medication and again at visit 4.

Sputum analysis

Participants will be asked to provide a baseline spontaneous sputum sample at visit 2. Participants who are productive of only a small volume of sputum or have difficulty expectorating will be asked to provide a baseline sputum sample within one week of visit 2. Samples are also required at visits 3 and 4.

Sputum will be processed using standardised guidelines in keeping with the European Respiratory Society Task Force document regarding sputum induction and processing.^{96,97} Spontaneous sputum specimens (sputum plus saliva) will be obtained at visit 2. If participants are unable to provide a sputum sample at visit 3 or 4, induced sputum samples will be collected (see below); samples will be processed within 2 to 4 hours of collection.

Sputum supernatant for measurement of neutrophil elastase, cytokines, hs-CRP and total antioxidant capacity will be separated and frozen at -70°C for measurement at the completion of the study.

Induction of sputum

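### No pregnancy test is scheduled between the pre-dose test at visit 2 and the end of dosing at visit 4, although pregnancy is a reason to stop study drug and 8 weeks of drug are handed out at visit 3

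*Protocol*

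**What the plan says.** The exclusion criteria bar pregnant or lactating women, and the section on reasons for discontinuing study medication includes pregnancy: "Risk to subject, as judged by the investigator - Pregnancy".

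The section on simple blood tests provides a serum test at screening for women of child-bearing potential and then: "A urinary pregnancy test will be done at visit 2 prior to commencement of study medication and again at visit 4". In the schedule table, the row beginning "Pregnancy test if applicable (blood" is marked at visits 1 and 4, and the row "Urinary pregnancy test" is marked at visits 2 and 4. Both rows are blank at visit 3.

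Under test drug dispensing, participants receive 4 weeks of capsules at visit 2 and a supply "for a further 8 weeks at visit 3, according to the dosage regime to which they are allocated". Visit 3 is at week 4; visit 4, at week 12, is the end of the 12-week treatment period.

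Three other contacts during dosing could bring a pregnancy to light:

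- the open adverse-event question, "Has there been any change in your health since I last saw you";
- the physical examination, which "will be done by an investigator at all study visits";
- the telephone calls at weeks 2 and 8, whose purposes include "to discuss adherence to study medication, and to record any exacerbations or adverse events".

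**The concern.** A stopping reason is useful only if the event can come to attention while there is still treatment to stop. The next scheduled pregnancy test after the first dose falls at week 12, when dosing ends.

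Two groups of participants are affected: those who conceive during the first weeks of dosing, and those who conceived too shortly before visit 2 for that test to be positive. Either can be resupplied at week 4 without a test. If she does not know she is pregnant, or does not mention it, she may take up to 8 more weeks of a product that the protocol says should be stopped. The stake is avoidable exposure in pregnancy. Nothing here bears on the primary endpoint, the sample size or the significance level.

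**Working it through.** The protocol gives no figure for this point, so there is none to reproduce. The check compares the text with the table and then sizes the gap.

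**Timing of tests against dosing**

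| Visit | Week | Blood test (table) | Urine test (table) | Test in text | Drug issued |
|---|---|---|---|---|---|
| 1 | -4 to -2 | yes | no | serum | none |
| 2 | 0 | no | yes | urine, pre-dose | 4 weeks |
| 3 | 4 | no | no | none | 8 weeks |
| 4 | 12 | yes | yes | urine | none |

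Text and table agree that visit 3 has no test. The untested interval on treatment is 12 - 0 = 12 weeks, which is the whole course. The only disagreement is at visit 4, where the table has a blood and a urine test and the text has urine alone.

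**Size of the untested resupply**

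- 8 weeks x 7 days = 56 days
- 500 mg twice daily: 56 x 2 = 112 capsules
- 1000 mg twice daily: 56 x 4 = 224 capsules
- Share of the course: 8/12 = 67%

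**What a visit 3 test would achieve**

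Assumptions, none from the protocol: conception is spread evenly over time, a urine test turns positive L weeks after conception with L between 1 and 3, and nobody self-reports.

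- Pregnancies exposed to drug but not detectable at visit 2 are conceived between week -L and week 12, a span of 12 + L weeks.
- Visit 3 detects those conceived between week -L and week 4 - L, a span of 4 weeks. The share caught is 4/(12 + L).
- Exposure is 12 weeks for each conception before week 0 (12L in total). It is 12 - t weeks for a conception at week t, which adds up to 12 x 12/2 = 72 over weeks 0 to 12. Total: 72 + 12L.
- Each pregnancy caught at visit 3 avoids 8 weeks: 4 x 8 = 32. The share of drug-weeks avoided is 32/(72 + 12L).

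| L (weeks) | Share caught | Drug-weeks avoided |
|---|---|---|
| 1 | 4/13 = 31% | 32/84 = 38% |
| 2 | 4/14 = 29% | 32/96 = 33% |
| 3 | 4/15 = 27% | 32/108 = 30% |

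**Expected numbers in this trial**

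Further assumptions: 5 to 20 of the 40 participants are women of child-bearing potential, and 2% to 10% of them would conceive per year.

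- Exposed pregnancies, low: 5 x 0.02 x 13/52 = 0.025
- Exposed pregnancies, high: 20 x 0.10 x 15/52 = 0.58
- Caught at visit 3, low: 5 x 0.02 x 4/52 = 0.008
- Caught at visit 3, high: 20 x 0.10 x 4/52 = 0.15

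**The case against.** The strongest reply is that this is a preference about how often to test. Text and table agree that visit 3 has no test, so nothing is contradicted. A list of discontinuation reasons says what to do once an event is known; it does not promise surveillance for each item.

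Pregnancy control is also not absent. Two tests precede the first dose, 2 to 4 weeks apart. During dosing there are two calls, open questioning, an examination that includes the abdomen, and an alert card with study contact numbers. The consent pages are not in the document reviewed and may tell participants to avoid or report pregnancy. The protocol cites no reproductive toxicity. Even at the top of the assumed ranges, a visit 3 test would catch 0.15 pregnancies in the whole trial and would miss about 70% of those exposed.

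Much of this stands. It is a weak safety schedule and not an inconsistency, the numbers are small, and the remedy is partial. The percentage of drug-weeks avoided is an upper figure, because some women would report a pregnancy themselves.

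What does not stand is the suggestion that the other contacts fill the gap. None is a pregnancy test, and the protocol specifies no pregnancy question at any of them. An examination at week 4 is unlikely to reveal a pregnancy only weeks old. The absence of cited fetal harm is not evidence of safety: the protocol's safety summary reports no pregnancy data, and the protocol itself decided that pregnancy should stop treatment.

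**Conclusion.** The concern holds. No scheduled pregnancy test can trigger the stopping reason while drug remains to be stopped, and two-thirds of the course is issued at visit 3 without one. This is established directly from the text and the table.

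The benefit of a visit 3 test is modest: roughly 27% to 31% of exposed pregnancies caught and 30% to 38% of their drug-weeks avoided, in a trial where well under one exposed pregnancy is expected. Those figures rest on the assumed detection lag, even conception over time and no self-report; the expected counts also rest on assumed enrolment and conception rates. The case for change is that the event is rare but potentially serious, the protocol already requires drug to stop for it, and the remedy is nearly free. It should be changed on participant-safety grounds. The blood-or-urine mismatch at visit 4 is clerical and adds no weight.

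**What to change.** For women of child-bearing potential, add a urine pregnancy test at visit 3, with the result known before the 8-week supply is issued. Keep one pregnancy test at visit 4, and make the table and the text agree on whether it is blood or urine.

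The cost is one sentence in the section on simple blood tests, one mark in the schedule table, and at most one dipstick per eligible woman at a visit she already attends. If the table's second visit 4 test is dropped, the number of tests in the table does not rise. A participant who stops drug for a positive result can still attend visit 4, since the protocol already asks those who discontinue to complete the study where possible.

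The longest untested interval on treatment falls from 12 weeks to 8. Conceptions too late to be detectable at week 4 would still go untested until week 12.
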